EUS-guided tissue acquisition of pancreatic masses is the main modality for the diagnosis of pancreatic solid tumors including adenocarcinoma and neuroendocrine tumor. Traditionally, this is done through sampling with fine needle aspiration (FNA); however, this approach has led to variable diagnostic yield with approximately 20% of the samples being non-diagnostic¹⁻³ needing repeat procedures. Several tertiary centers worldwide have adopted rapid on-site evaluation (ROSE) of cytopathology, where a cytopathologist is at the bedside of the procedure and looking at each samples in real-time to give feedback to the endoscopists in terms of adequacy and preliminary diagnosis of their EUS-guided FNA. ROSE has been shown to increase the diagnostic yield by 10 to 15%¹ ⁴. Although currently unavailable at most Canadian sites, hospitals have been contemplating the implementation of ROSE in hopes of improving care for patients with pancreatic cancer and to prevent the need for repeat procedures and its associated costs and potential adverse events. Recently, however, novel core biopsy needles have been developed for fine needle biopsy (FNB) and histological assessment⁵. These needles allow for the acquisition of core samples with intact tissue architecture enabling immunohistochemical staining thereby enhancing the diagnostic yield. Although some studies suggest that FNB alone may be just as effective as FNA with ROSE, there are no comparative outcomes trials. As such, the goal of our study is to compare EUS-FNB with core needle sampling alone vs. EUS-FNA with ROSE in pancreatic solid lesions. If shown to be equivalent, FNB could potentially obviate the need for ROSE and be implemented in a more readily and affordable fashion across Canada.

Objectives:

Aim: To compare the diagnostic accuracy of EUS-FNB alone vs. EUS-FNA with ROSE in patients with solid pancreatic masses suspected to be of malignant origin.

Hypothesis: EUS-FNB is non-inferior to EUS-FNA with ROSE in the diagnostic accuracy for solid pancreatic masses while being associated with fewer needle passes and shorter procedure time.

Primary outcomes

- Diagnostic accuracy defined as (true positive + true negative)/all samples
- Final diagnosis will be based on the following criteria
- A) Final diagnosis of malignancy (one of the following):
 - histological evidence of malignancy on the corresponding subsequent surgical specimen
 - presence of an unresectable lesion during subsequent surgery

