 - malignant cytology/pathology on EUS-sampling followed by documented locoregional progression/development of metastases on follow-up axial imaging.
- B) Final diagnosis of benign pancreatic mass (one of the following):
 - surgical pathology or exploration showing the absence of malignancy

- follow-up imaging at > 6 months reporting stability of the pancreatic lesion
- cytological or histopathological diagnosis of benign disease with an appropriate clinical course of disease for minimum of 6 months

Secondary Outcomes

- Diagnostic characteristics: sensitivity, specificity, positive and negative predictive value
- Specimen adequacy: defined as the proportion of samples in which a final histopathological diagnosis could be made
- Median number of needle passes, procedural time
- Rate of procedure-related adverse events with severity graded as per the ASGE lexicon⁶
- Cost-effectiveness

Methods:

EUS procedure:

Procedures are performed with a linear echoendoscope under conscious sedation. EUS-FNB is performed with a 22 gauge Core-needle. Tissue sampling technique is standardized between the endoscopists. Two passes are performed using the core needle. The biopsied samples are then expressed using a stylet into a jar filled with 10% formalin. A third pass is allowed if, on macroscopic inspection of the acquired sample, the specimen is deemed insufficient by the endoscopist. EUS-FNA with ROSE is performed with a 22 gauge FNA needle. The sampled specimen is expressed into a glass slide with a stylet; then using another glass slide the sample is spread out to make smears on two slides. Each pair of slides is then numbered according to their respective needle passes. One slide is air dried and stained with modified Giemsa stain for ROSE, while the other slide is fixed in 95% ethanol and later coated with with Pananicolaou stain.

This is a multi-center, randomized, single blinded, non-inferiority, trial comparing EUS-FNB alone to EUS-FNA with ROSE in the diagnosis of solid pancreatic masses. Following consent, patients are randomized, at the time of the procedure, to undergo either EUS-FNB alone or EUS-FNA with ROSE. The randomization sequence will be generated by a computerized randomization scheme using a block size of 10 stratified according to the endoscopist.

Inclusion Criteria:

- 1. Age > 18 years

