- 2. Patients referred for EUS evaluation of a definite solid pancreatic mass noted on CT/MRI/EUS, in which malignancy is suspected with no previous histological diagnosis

Exclusion Criteria: 1.

- 1. Age < 18 years, pregnant patients
- 2. Uncorrectable coagulopathy PT>50% of control, PTT>50 sec, or INR>1.5 and/or uncorrectable thrombocytopenia platelet count<50, 000109/L.

Feasibility: The primary analysis is a noninferiority comparison of EUS-FNB vs. EUS-FNA with ROSE in terms of diagnostic accuracy, which, according to the most recent literature, is approximately 90% for both modalities. The margin of noninferiority is set at 10% in accordance with the USFDA recommendations. To achieve a statistical power of 80% with a two-sided type I error of 5%, a total of 224 patients (112 per group) is needed. Assuming a 5% dropout rate, a final sample size of 236 (118 per group) is estimated. The study is anticipated to take 2 years to complete.

Analysis: An intention-to-treat analysis will be carried out. The noninferiority hypothesis for the primary outcome will be assessed using the Z-test with a 95% two-sided confidence interval of the difference in the diagnostic accuracy and the margin of noninferiority. Interim analysis is planned after 50% of the cohort is recruited. If a > 20% difference in sensitivity is found between both methods then the study will be terminated early. Exploratory imaging and patient predictors of a diagnostic sampling is carried out using standard multivariable logistic regression analysis.

Cost-effectiveness:

A decision tree will be created for the two possible sampling approaches. Probability assumptions will be extracted from the RCT. Costs will be determined from the RAMQ. Third-party costs related to the procedure and downstream management costs will be determined based on the RCT resource utilization data. Deterministic and probabilistic sensitivity analyses will be undertaken.

Patient follow-up:

Patients will be contacted by telephone interview at 48-72 hours post procedure to ensure that no adverse events have occurred. All other follow-up will be standard of care and at the discretion of the treating physician.

Anticipated results:

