We anticipate that the results will show that EUS-FNB alone will be non-inferior to EUS-FNA with ROSE in the diagnostic accuracy of solid pancreatic masses. We also expect that both modalities will have similar diagnostic characteristics such as sensitivity, specificity, and positive and negative predictive value. Finally, the use of EUS-FNB will likely be associated with fewer needle passes, shorter procedure time, and be more cost-effective.

If our data is consistent with the anticipated results then it would have a large impact on improving diagnostic yield of EUS tissue acquisition in pancreatic mass and potentially obviate the need for on-site cytopathology at a time where centers across Canada are contemplating the addition of this effective but expensive and resource intensive modality.

MULTICENTER GUIDELINES

Protocol Chair

The Protocol Chair is responsible for performing the following tasks:

- Coordinating, developing, submitting, and obtaining approval for the protocol as well as its subsequent amendments
- Assuring that all participating institutions are using the correct version of the protocol.
- Taking responsibility for the overall conduct of the study at all participating institutions and for monitoring the progress of the study.
- Reviewing and ensuring reporting of Serious Adverse Events (SAE)
- Reviewing data from all sites

Coordinating Center

The Coordinating Center is responsible for performing the following tasks:

- Ensuring that REB approval has been obtained at each participating site prior to the first patient registration at that site, and maintaining copies of REB approvals from each site.
- Managing central patient registration.
- Collecting and compiling data from each site.
- Establishing procedures for documentation, reporting, and submitting of AE's and SAE's to the Protocol Chair, and all applicable parties.
- Facilitating audits by securing selected source documents and research records from participating sites for audit, or by auditing at participating sites.

Participating Sites

Participating sites are responsible for performing the following tasks:

- Following the protocol as written
- Submitting data to the Coordinating Center.
- Providing sufficient experienced clinical and administrative staff and adequate facilities and equipment to conduct a collaborative trial according to the protocol.
- Maintaining regulatory binders on site and providing copies of all required documents to the Coordinating Center.

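### A single block size of 10, printed in the protocol and applied within each unblinded endoscopist's own list, lets an operator who keeps count be certain of about 1 in 6 allocations on average in full blocks

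*Protocol*

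**What the plan says.** The randomisation paragraph in the protocol's Methods says that the sequence is computer-generated "using a block size of 10 stratified according to the endoscopist". Allocation takes place late: "Following consent, patients are randomized, at the time of the procedure". Among the Coordinating Center's tasks is "Managing central patient registration".

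The same text is in use everywhere. The Protocol Chair's duties include "Assuring that all participating institutions are using the correct version of the protocol", and participating sites must follow it.

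The trial is called single blinded, without naming the blinded party. The procedures rule out the endoscopist. The two arms use different needles and different specimen handling. In the FNB arm, "A third pass is allowed if, on macroscopic inspection of the acquired sample, the specimen is deemed insufficient by the endoscopist". In the other arm ROSE is used, which the introduction describes as a setting "where a cytopathologist is at the bedside of the procedure".

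For the primary comparison, the Analysis section states: "An intention-to-treat analysis will be carried out".

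**The concern.** Three features coincide. The block size is fixed and disclosed, each stratum is one operator's own list, and that operator sees every past allocation in it. Once five patients in a block have gone to one arm, the rest of that block is known. The operator does not need access to the list; a tally is enough.

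An endoscopist who knows the next arm could delay or bring forward a patient, or not approach one, according to how hard the mass looks to sample. The arms could then differ in case difficulty, in either direction, in a non-inferiority trial with a 10-point margin on accuracy. Intention-to-treat takes the patients as randomised, so it can neither detect nor correct selection that happened before randomisation.

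**Working it through.** **Inputs from the protocol.** Block size 10, stratified by endoscopist (Methods). Final sample size 236, 118 per group (Feasibility). Equal groups imply 1:1 allocation, hence 5 + 5 in each block. The plan's own total follows from its dropout step: 224 / 0.95 = 235.8, rounded to 236. It serves here only as the denominator. **Assumption:** the number of endoscopists, K, is not given, so a range is shown.

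**Step 1: when is an allocation certain?** Position j is certain if one arm already has all five of its places among the first j - 1. With C(10,5) = 252 equally likely blocks, P(j certain) = 2 x C(j-1, 5) / 252.

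| Position | Calculation | Probability |
|---|---|---|
| 1-5 | not possible | 0 |
| 6 | 2 x 1 / 252 | 0.008 |
| 7 | 2 x 6 / 252 | 0.048 |
| 8 | 2 x 21 / 252 | 0.167 |
| 9 | 2 x 56 / 252 | 0.444 |
| 10 | 2 x 126 / 252 | 1.000 |

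The sum is 420 / 252 = 1.667 per block, or 16.7%. Enumerating all 252 blocks gives the same value. It is an average: one complete block yields at least 1 and at most 5 certain allocations.

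**Step 2: best guessing.** Always naming the arm with more places left gives an expected 5 + (2^10 / 252 - 1) / 2 = 5 + (4.063 - 1) / 2 = 6.53 correct of 10, or 65.3%, against 50% by chance.

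**Step 3: unfilled last blocks.** An endoscopist with n patients contributes 1.667 for each full block plus the sum of the Step 1 probabilities over the remaining positions (0.008 for six remaining patients, 0.056 for seven, 0.222 for eight, 0.667 for nine). Splitting 236 evenly:

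| K | Patients each | Expected certain allocations | Share of 236 |
|---|---|---|---|
| 4 | 59 | 4 x (5 x 1.667 + 0.667) = 36.0 | 15.3% |
| 14 | 16 or 17 | 2 x 1.675 + 12 x 1.722 = 24.0 | 10.2% |
| 23 | 10 or 11 | 23 x 1.667 = 38.3 | 16.2% |
| 24 | 9 or 10 | 20 x 1.667 + 4 x 0.667 = 36.0 | 15.3% |
| 30 | 7 or 8 | 26 x 0.222 + 4 x 0.056 = 6.0 | 2.5% |

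Over every K from 4 to 24, the lowest value is at 14 and the highest at 23. Above 25 the share drops because few operators complete a block: 8.2% at 26 and 0.1% at 40. Uneven loads soften that drop, because busy operators still fill blocks. Simulated uneven loads average 14.1% at K = 10, 11.8% at K = 20 and 9.8% at K = 30.

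**Step 4: alternatives.** For a fixed block of 2m the certain share is 1/(m+1): 33.3% for size 4, 25.0% for 6 and 20.0% for 8. Smaller fixed blocks are therefore worse than 10. For sizes drawn at random from 8, 10, 12 and 14, facing an optimal guesser who knows that set (2,500 simulated runs):

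| Patients per endoscopist | Certain | Best guessing correct |
|---|---|---|
| 10 | 0.1% | 61.7% |
| 20 | 1.0% | 62.9% |
| 30 | 0.9% | 63.6% |
| 60 | 0.8% | 64.2% |

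Guessing above chance falls from 15.3 points to between 11.7 and 14.2 points, a reduction of about 7% to 24%.

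**The case against.** The strongest reply is that the design leaves little room to act on a prediction. Patients arrive by referral with a definite mass. The listed exclusions are narrow: age, pregnancy, and coagulation or platelet limits. Randomisation follows consent and happens at the procedure, registration is central, and both arms are described as standard care. All of this stands, and it limits the risk. It does not close it. The next arm can be worked out before a patient is approached or scheduled. The qualifying mass may be one noted at EUS itself, and suspicion of malignancy is a judgement. Central registration cannot hide what follows from a printed block size.

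It is also fair to say that 10 is a better choice than smaller fixed blocks, that the operator must know the size and keep count, and that the share depends on a number of endoscopists that the protocol does not give.

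One could add that randomisation details may sit in another document. That would answer a complaint that the protocol is silent on how the list is concealed, and no such complaint is made here. The block size is something the protocol itself states.

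**Conclusion.** The point holds as an avoidable weakness in a stated method. In full blocks an operator who counts is certain of 16.7% of allocations on average and guesses 65% correctly. Across the trial this is an expected 24 to 38 of 236 (10-16%) if there are 4 to 24 endoscopists with even loads, and much less if most operators enrol fewer than ten patients.

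Four stronger readings are not supported:

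- **That 1 in 6, or 38 of 236, is a maximum.** Both are expected values, and realised counts can be higher.
- **That the comparison is biased.** Nothing in the protocol shows that any operator would steer patients, or in which direction, and it gives no accuracy difference between easy and hard masses. As an illustration only, assume a difference of 5 to 10 points and every certain slot steered toward the same arm. The shift would be between 0.102 x 5 = 0.5 and 0.167 x 10 = 1.7 points, against the 10-point margin. Opposing preferences would partly cancel; acting on uncertain guesses would add.
- **That varying the block size removes most of the predictability.** It removes nearly all certain allocations, but best guessing stays at about 62-64%.
- **That the protocol contradicts itself here, or that blocks of 10 are too large.** Neither is so. The problem is a fixed and disclosed size within an unblinded operator's stratum.

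**What to change.** Replace the randomisation sentence with:

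> The randomization sequence will be computer-generated in permuted blocks of randomly varying size, stratified by endoscopist; block sizes are held by the Coordinating Center and not disclosed to participating sites.

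Keep the sizes themselves out of the protocol, since every site holds it. If recruitment has begun, apply the change to unopened blocks only. Do not move to small blocks; a set such as 8, 10, 12 and 14 is suitable.

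The cost is one replaced sentence and new allocation lists, with no extra patients. The downside is that the largest possible imbalance within one endoscopist's unfinished block rises from 5 (half of 10) to 7 (half of 14).

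Two optional additions address the predictability that remains; the point does not depend on them. First, have eligibility confirmed with the Coordinating Center before the allocation is released, which may overlap with the existing central registration. Second, keep a screening log by endoscopist that includes eligible patients who were not approached as well as those who consented but were not randomised. A log of the second group alone would miss the selection described above. The cost is one entry per patient.

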- Collecting and submitting data according to the schedule specified by the protocol.

ANTICIPATED RISKS

We do not anticipate major risk or discomfort beyond that associated with the conventional procedure. Both EUS-FNA with ROSE and FNB alone are part of standard or care. The following are conventional risks associated with EUS-FNA or FNB.

- 1) Perforation: Only physicians specially trained in EUS will be performing these procedures. The exact risk is minimal (<1%).
- 2) Infection: It is not standard practice to give antibiotics to all patients prophylactically for either percutaneous liver biopsy or EUS-FNA of noncystic lesions. Therefore, no subjects will receive antibiotics prophylactically for EUS sampling except those patients at risk for infective endocarditis according to American Heart Association guidelines.
- 3) Bleeding: The exact risk is minimal (1 in 5,000 chance). Doppler examination will be performed under EUS guidance prior to biopsy to ensure that the needle does not traverse a blood vessel. As a precautionary measure,

furthermore, all patients will have PTT, PT/INR, hemoglobin, and platelet count checked prior to the procedure. Those below acceptable standards will not be offered inclusion into the study. Frequent vital signs will be measured and recorded. If vital signs are abnormal and prolonged, a repeat CBC and possibly CT scan will be performed after procedure to ensure the absence of internal or external hemorrhage. These measures should ensure any clinically significant hemorrhage is detected and treated in a timely manner.

- 4) Pancreatitis (risk: 1%): Will be detected by the presence of pain with or without nausea and vomiting after pancreatic biopsy. If present, the patient will be hospitalized, kept NPO, and receive IV hydration.
- a. Steps taken to minimize the risks.
 Adherence to the standard of practice of EUS-guided tissue sampling at the McGill University Health Center as outlined above
- b. Financial risks to the participants. None.

ADVERSE EVENT REPORTING

Definition of Adverse Event (AE)

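### Exclusion 2 misstates its prothrombin time limit: taken literally, a normal result meets it, and it conflicts with the INR limit beside it (minor)

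*Protocol*

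**What the plan says.** Item 2 of the protocol's Exclusion Criteria sets its clotting and platelet limits as "Uncorrectable coagulopathy PT>50% of control, PTT>50 sec, or INR>1.5 and/or uncorrectable thrombocytopenia platelet count<50, 000109/L". The limits are alternatives, so meeting one is enough. They are the only figures given for either label.

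Anticipated Risks, item 3 (Bleeding), makes testing a precaution: "all patients will have PTT, PT/INR, hemoglobin, and platelet count checked prior to the procedure". It continues: "Those below acceptable standards will not be offered inclusion into the study". It does not state what those standards are.

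The trial is multi-center (Methods), and the Participating Sites list under Multicenter Guidelines holds each site to the protocol as it is written.

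**The concern.** The PT limb points the wrong way for a limit meant to detect impaired clotting. A PT equal to control is 100% of control, which is above 50%. The same blood sample therefore meets the PT limb and passes the INR limb next to it, although either limb alone is enough to exclude.

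This is the protocol's only numerical bleeding gate, and it is applied to every patient before a needle puncture. A site cannot use the PT limb literally, so it has to decide for itself what was meant. Different sites may then screen by different PT rules without any record of it. On a strict audit, an enrolled patient with a normal PT could be listed as an eligibility deviation.

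**Working it through.** **Inputs from the protocol.** PT above 50% of control, INR above 1.5, and the platelet string (Exclusion Criteria, item 2); 236 patients (Feasibility); bleeding risk of 1 in 5,000 (Anticipated Risks, item 3).

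**Assumptions, not in the protocol.** INR = (PT/control)^ISI, with ISI tried from 0.9 to 2.0; a normal PT is about 100% of control, and normal PT activity is about 100%.

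**Step 1: the PT limb read literally.** The limb is met when PT/control > 0.5. A normal patient has PT/control of about 1.0, so the limb is met. The matching INR is 1.0^ISI = 1.0, which does not exceed 1.5, so the INR limb is not met.

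**Step 2: both limits on one scale.**

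| ISI | INR when PT is 50% of control | PT (% of control) when INR is 1.5 | INR when PT is 150% of control |
|---|---|---|---|
| 0.9 | 0.536 | 156.9 | 1.440 |
| 1.0 | 0.500 | 150.0 | 1.500 |
| 1.2 | 0.435 | 140.2 | 1.627 |
| 1.5 | 0.354 | 131.0 | 1.837 |
| 2.0 | 0.250 | 122.5 | 2.250 |

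At ISI 1 the literal PT limit equals INR 0.5, and 1.5 / 0.5 = 3. Over the whole range it equals INR 0.54 down to 0.25, so it agrees with 1.5 at no ISI tried.

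**Step 3: other readings of the 50%.**
- As PT activity, normal (about 100%) still exceeds 50%. To pick out abnormal patients, the printed inequality would have to be reversed.
- As an excess over control, PT/control > 1.5. This matches the INR limb at ISI 1, and corresponds to INR 1.44 to 2.25 over ISI 0.9 to 2.0 (last column). It needs a word that is not in the text.

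The protocol does not choose between these readings, and they need not select the same patients.

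**Step 4: the Bleeding item.** It names the tests but gives no limits, so it cannot repair item 2. It excludes patients below the standards, whereas item 2 excludes high values of PT, PTT and INR. Only the platelet limit excludes low values.

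**Step 5: platelets, as a check only.** If the run of characters at the end is 10^9/L with a lost superscript, the limit is 50,000 × 10^9/L, or 50,000,000 per microlitre. By contrast, 50,000 per microlitre is 50 × 10^9/L. The ratio is 50,000 / 50 = 1,000. A decimal-comma reading (50.000 × 10^9/L) would remove the mismatch, but the protocol elsewhere uses the comma for thousands ("The exact risk is minimal (1 in 5,000 chance") and the point for decimals ("PTT>50 sec, or INR>1.5"). The extracted string cannot settle what is printed on the page.

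**Step 6: reach of the consequence.** At the protocol's own rate, expected bleeds are 236 × 1/5,000 = 0.047, or about 0.05 in the whole trial.

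**The case against.** The strongest reply is that the numbers do not stand alone. They qualify an uncorrectable coagulopathy and an uncorrectable thrombocytopenia, and a patient with normal clotting and platelets has neither. This stands as to intent. A reader might infer that the protocol shuts out every normal patient; read as a whole, it does not support that, and sites would probably not act that way. But the label supplies no PT limit. It shows that the printed limit is not meant literally and leaves the site to find another.

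A second reply is that one missing word would bring the PT and INR limbs into line. At ISI 1 that is correct (Step 3). It shows that the repair is easy, but not that the text already says so.

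Third, the word below in the Bleeding item may only mean failing to meet a standard. That is a fair reading. The item still gives no limits, which is the main point about it.

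Fourth, the platelet string is visibly damaged. This stands. A reader might infer a proven thousandfold error, but a stray space, a lost superscript and perhaps a lost multiplication sign rule out that conclusion until the source page is seen.

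Fifth, the effect on outcomes is slight. This also stands. A reader might infer that the adverse event rate would depend on the site, or that the comparison would be biased. Neither is supported. About 0.05 bleeds are expected on the protocol's own figure. Patients are randomized after consent, at the procedure, with stratification by endoscopist, so any local reading of eligibility applies to both arms alike.

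**Conclusion.** The point holds as a minor error of statement. The PT wording is intact text and is wrong as written: a normal PT meets it, and it contradicts the INR limb by a factor of three at ISI 1, with no agreement at any ISI from 0.9 to 2.0. The size of the gap rests on the assumed PT/INR relation. The direction rests only on a normal PT being about equal to control, or normal activity being about 100%.

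The practical impact is low. What remains is a safety criterion whose PT limit each site must supply for itself, and a Bleeding item that depends on limits it does not give. The platelet figure and unit are a matter to verify, not a finding in themselves.

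**What to change.** The sponsor's clinicians should restate the PT limb so that it agrees with the INR limb and a normal result does not meet the exclusion. The Bleeding item under Anticipated Risks should refer to the same limits and describe their direction consistently. The platelet figure and unit should be checked against the source page and corrected if they do not belong together. The screening form should then be updated to match. No value is proposed here; the choice is a clinical one.

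The cost is a one-line amendment and a form update. No patients or tests are added, because the protocol already has these tests done in everyone.

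### The 112 per group matches a one-sided 5% test; under the stated two-sided 5% error and 95% confidence interval, power is about 70%, not 80%

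*Protocol*

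**What the plan says.** The Feasibility paragraph gives every input to the sample size. Diagnostic accuracy "is approximately 90% for both modalities", the margin is 10%, and power is 80%. It then states that "with a two-sided type I error of 5%, a total of 224 patients (112 per group) is needed", and raises this to 236 (118 per group) for 5% dropout.

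The Analysis paragraph fixes the decision rule for the primary outcome: non-inferiority is "assessed using the Z-test with a 95% two-sided confidence interval of the difference in the diagnostic accuracy and the margin of noninferiority".

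The two paragraphs agree on the error rate: two-sided 5% in one, a 95% two-sided interval in the other. The protocol mentions neither a one-sided 5% test nor a 90% interval.

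**The concern.** A 95% two-sided interval compared with a non-inferiority margin is a one-sided test at 2.5%, with critical value 1.96. The sample size should be computed with that value. The figure of 112 per group looks too small for it and is what the formula returns with 1.645. If so, the number of patients and the planned test come from different designs, and the stated power belongs to a test that the protocol does not plan to run.

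Non-inferiority on accuracy is the primary comparison. Ethics boards and sites have been told that the trial has a 20% chance of missing non-inferiority when the two methods are equally accurate. If the real figure is nearer 30%, an inconclusive result is half as likely again as stated. The mismatch also leaves room for a later switch to a 90% interval, which would double the one-sided error from 2.5% to 5%.

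**Working it through.** **Inputs** (all from Feasibility, except the decision rule, which is from Analysis)
- Accuracy 0.90 in both arms, so the true difference is 0
- Margin 0.10, absolute
- Power 80%, z = 0.842
- Two-sided type I error 5%, with a 95% two-sided interval as decision rule, z = 1.960
- 1:1 allocation, 5% dropout

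**Formula** (unpooled normal approximation)

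n per group = (z_alpha + z_power)² × [2 × 0.9 × 0.1] / 0.10² = 18 × (z_alpha + 0.842)²

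**Reproducing the protocol's figure**
- With z_alpha = 1.645 (one-sided 5%, 90% interval): 18 × (2.486)² = 111.3, so 112 per group and 224 in total. This is exactly the protocol's number.
- Dropout: 224 / 0.95 = 235.8, so 236. This step is correct.

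**With the error rate the protocol states**
- With z_alpha = 1.960: 18 × (2.802)² = 141.3, so 142 per group and 284 in total.
- After 5% dropout: 284 / 0.95 = 298.9, so 299, or 300 when each group is rounded up (142 / 0.95 = 149.5, so 150).
- Shortfall before dropout: 142 − 112 = 30 per group, 60 in total.

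**Other formulas.** Results per group at one-sided 2.5% and 5%:

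| Method | 2.5% | 5% |
|---|---|---|
| Unpooled normal | 142 | 112 |
| Farrington-Manning | 155 | 122 |
| Continuity-corrected | 161 | 131 |
| Equivalence (two one-sided tests) | 190 | 155 |

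A superiority comparison of 90% with 80% needs 199 per group (two-sided 5%) or 157 (one-sided 5%). None of these gives 112 at two-sided 5%.

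**Power of the planned size**

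Power = Φ(0.10 / √(0.18 / n) − z_alpha)

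- n = 112, z = 1.960: Φ(2.494 − 1.960) = 70.3%
- n = 112, z = 1.645: Φ(2.494 − 1.645) = 80.2%
- n = 118, z = 1.960: Φ(2.560 − 1.960) = 72.6%

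Exact binomial enumeration of the Wald interval rule, with 90% in both arms:
- n = 112: 71.6% with a 95% interval, 80.3% with a 90% interval
- n = 118: 73.0% with a 95% interval
- n = 142: 80.6% with a 95% interval

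With a Farrington-Manning score test at one-sided 2.5%, power at 112 per group is 65.8%.

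**Sensitivity to the planning value** (n = 112, 95% interval, normal approximation, same accuracy in both arms)

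| Accuracy | Power |
|---|---|
| 88% | 63.4% |
| 89% | 66.7% |
| 90% | 70.3% |
| 91% | 74.4% |
| 92% | 78.8% |

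**The case against.** Four points can be made for the protocol.

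- **Validity is intact.** The 95% interval keeps the nominal chance of a false non-inferiority claim at 2.5% whatever the sample size. This stands: the error costs power only.
- **The 90% accuracy is only approximate.** With about 92.3% accuracy in both arms, 112 per group would reach 80% power under the 95% interval. This is correct, but the protocol gives no such value, and the sensitivity runs the other way as well. With the only planning value stated, 1.645 reproduces 112 without adjustment.
- **A one-sided 5% test may have been intended.** The protocol shows no formula, so the origin of 112 is inferred from an exact numerical match. If this was the intention, the stated error rate and the stated interval would both be wrong, and the text would still need correction.
- **Restating power does not add power.** This is true. It makes the protocol accurate but leaves the trial as likely to be inconclusive as before. Whether to enrol more patients is a separate decision for the sponsor.

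A separate statistical analysis plan would not settle the matter, because the protocol itself states a figure that does not follow from its own inputs.

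**Conclusion.** The concern holds. The 112 per group does not follow from the protocol's stated inputs, which require 142. Under the planned 95% two-sided interval, power is about 70% with 224 evaluable patients and about 73% if all 236 are evaluable, some 7 to 10 points below the stated 80%. The chance of missing non-inferiority when both methods are 90% accurate is about 27% to 30%, against the stated 20%.

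These figures rest on 90% accuracy in both arms, a 10-point absolute margin, and an unpooled (Wald) comparison. A score-type test would lower power further, to 65.8% at 112 per group. The type I error of the planned analysis is not affected.

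**What to change.** Keep the 95% two-sided interval and the planned 236 patients. In Feasibility, replace the 80% claim with the power the design has: about 70% with 224 evaluable patients, and about 73% if all 236 are evaluable, assuming 90% accuracy in both arms. The cost is wording only, plus a less favourable stated power.

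If the sponsor wants to keep 80% power with the 95% interval, the size has to rise to 284 evaluable patients, about 300 enrolled, which is 64 more than planned. Declaring a one-sided 5% test with a matching 90% interval would also make the paragraphs agree. However, it doubles the chance of a false non-inferiority claim, so it would need its own justification, and I would not choose it merely to preserve the number 224. Whichever course is taken, it should be fixed before any comparative data are seen, including at the planned interim analysis.
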